3.5.2.4 Tumor Lysis Syndrome (TLS)

TLS, including fatal cases, has been reported in patients receiving obinutuzumab. Patients with high tumor burden, high circulating lymphocyte count (> 25 X 10⁹/L) or renal impairment are at greater risk for TLS and should receive appropriate tumor lysis prophylaxis with antihyperuricemics (e.g., allopurinol or rasburicase) and hydration prior to the infusion of obinutuzumab. Continue prophylaxis prior to each subsequent obinutuzumab infusion, as needed.

During the initial days of obinutuzumab treatment, monitor the laboratory parameters of patients considered at risk for TLS. For treatment of TLS, correct electrolyte abnormalities, monitor renal function and fluid balance, and administer supportive care, including dialysis as indicated.

3.5.2.5 Infections

Serious, bacterial, fungal, and new or reactivated viral infections can occur during and following the completion of obinutuzumab therapy. Fatal infections have been reported. Do not administer obinutuzumab to patients with an active infection. Patients with a history of recurring or chronic infections may be at increased risk of infection.

Non-neutropenic patients who require antibiotic treatment may continue therapy with rhIL-15 and obinutuzumab.

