2.1.2 Exclusion Criteria

- 2.1.2.1 Current or prior anti-cancer treatment prior to the first dose of rhIL-15 as defined below:
 - Chemotherapy, targeted small molecule therapy, or other anti-cancer treatment not otherwise specified below within 2 weeks
 - Radiation therapy within 2 weeks
 - Anti-cancer monoclonal antibody (mAb) treatment within 4 weeks
 - Use of an investigational agent (e.g., biologic, drug, or other) within 4 weeks
 - Allogeneic stem cell transplant within 100 days
 - Systemic treatment for graft versus host disease (GVHD), including but not limited to oral or parenteral corticosteroids, ibrutinib, and extracorporeal phototherapy, within the last 12 weeks
- 2.1.2.2 Persisting toxicity related to prior therapy (including GVHD) of grade > 1, with the exception of the following: alopecia or sensory neuropathy grade ≤ 2 , or other grade ≤ 2 not constituting a safety risk based on investigator's judgment

Version Date: 09/14/2021

2.1.2.3 Current use of immunosuppressive medication, EXCEPT for the following:

- Intranasal, inhaled, topical steroids, or local steroid injection (e.g., intra-articular injection);
- Systemic corticosteroids at physiologic doses ≤ 10 mg/day of prednisone or equivalent; or,
- Steroids as premedication for hypersensitivity reactions (e.g., CT scan premedication)
- 2.1.2.4 Presence of Richter's transformation.
- 2.1.2.5 Patients requiring immediate cytoreduction, if they had no prior treatment with a drug that has an established clinical benefit.
- 2.1.2.6 Presence of uncontrolled intercurrent illnesses including but not limited to ongoing or active infection, symptomatic congestive heart failure, unstable angina pectoris, cardiac arrhythmia, cognitive impairment, active substance abuse, or psychiatric illness/social situations that in the view of the Investigator would preclude safe treatment and limit compliance with study requirements
- 2.1.2.7 Presence of active bacterial infections, documented HIV infection, PCR evidence for active or chronic hepatitis B or hepatitis C, or positive screening HBV/HCV serology without documentation of successful curative treatment (see Section 3.5.2.1 for data on obinutuzumab administration in patients with HBV, and Section 12.5 for IL-15 administration in HIV-positive patients)

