3 STUDY IMPLEMENTATION

3.1 STUDY DESIGN

To determine the MTD, and safety and toxicity profile of the combination of civ IL-15 and obinutuzumab, a non-randomized, open-label, single arm, single institution Phase I study will be conducted at the NCI. Each cycle of treatment is 28 days or 4 weeks, and a maximum of 6 cycles will be administered. Patients will be treated with civ IL-15 at dose levels of 0.5,1 or 2 mcg/kg/day on days 1-5 of cycles 1-6. Obinutuzumab (IV) will be administered at a dose of 100 mg on day 4, 900 mg on day 5, 1,000 mg on day 11, and 1,000 mg on day 18 of cycle 1; then 1,000 mg on day 4 of each subsequent cycle.

Study treatment will continue for as long as:

- Subject is deriving clinical benefit (complete remission [CR], partial remission [PR], or stable disease [SD]), and
- Subject is not experiencing any unacceptable toxicity (i.e., dose-limiting toxicity as found in Section 3.2 or toxicity requiring hold as defined in Section 3.5 lasting longer than two weeks)

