3.2 Dose-Limiting Toxicity

Dose-limiting toxicities are defined as: any grade 3, 4, or 5 toxicity if not incontrovertibly due to disease progression or an extraneous cause, and deemed possibly, probably or definitely related to IL-15 or obinutuzumab by the PI or designee during the first 28 days of treatment, with the following exceptions:

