3.4.3 Antimicrobial Prophylaxis

Patients with Grade 3 to 4 neutropenia lasting more than one week will receive antimicrobial prophylaxis until resolution of neutropenia to Grade 1 or 2. Antiviral and antifungal prophylaxis will be considered in patients with history of viral and fungal infections.

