3.5.2 Obinutuzumab-specific Adverse Events

Important risks identified in clinical investigations with obinutuzumab were: IRRs, TLS, thrombocytopenia (including acute thrombocytopenia), neutropenia (including prolonged and late onset neutropenia), prolonged B-cell depletion, infections (including hepatitis B reactivation and PML), worsening of pre-existing cardiac conditions GI perforation, and secondary malignancies. Obinutuzumab dose may be held as specified below, but not otherwise modified.

Version Date: 09/14/2021

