3.10.1 Criteria for Removal from Protocol Therapy

- Completed planned treatment regimen/duration (i.e., up to 6 cycles)
- Confirmed hematologic or radiographic disease progression
- Unacceptable toxicity occurring at any time during treatment as listed in Section 3.2 or those toxicities listed in Section 3.5 that require treatment to be stopped.
- Intercurrent illness that prevents further administration of treatment
- Requirement for use of prohibited therapies as listed in Section 4.2
- Pregnancy
- Subject's requests to be withdrawn from protocol therapy
- Noncompliance with trial treatment or procedure requirements that requires removal in the opinion of the PI
- Investigator's decision to withdraw the subject
- Study is cancelled for any reason

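### Section 3.5.2.5 both bars and permits obinutuzumab for a non-neutropenic patient on antibiotics for a still-active infection, and no section says which sentence governs

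*Combined protocol and SAP*

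**What the plan says.** Section 3.5.2.5 (Infections) describes the infection risk of obinutuzumab, notes that deaths have occurred, and then instructs: "Do not administer obinutuzumab to patients with an active infection". The instruction is not limited by grade, organism, neutrophil count or whether the infection is being treated.

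A separate closing paragraph of the same section reads: "Non-neutropenic patients who require antibiotic treatment may continue therapy with rhIL-15 and obinutuzumab". It does not require the infection to be controlled, and no linking word presents it as an exception.

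This is operative dosing text. The opening of section 3.5.2 says: "Obinutuzumab dose may be held as specified below, but not otherwise modified". The investigator must therefore look in the subsections that follow to learn when infection calls for a hold.

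**The concern.** Consider a non-neutropenic patient who develops a bacterial infection on treatment, starts antibiotics, and still has active infection when the next obinutuzumab infusion falls due. The first sentence says not to give it; the last says treatment may go on. An investigator who relies on the last sentence could give a B-cell-depleting antibody in the situation the first sentence rules out, and two investigators could treat the same patient differently while each citing the protocol.

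The choice also touches the dose-finding data. Section 3.1 counts a toxicity hold under section 3.5 of more than two weeks as unacceptable toxicity. Sections 3.3 and 10.2 replace a patient without a DLT who does not finish treatment in the DLT window. The rule followed for a day 11 or day 18 dose in cycle 1 may therefore affect whether that patient counts towards the maximum tolerated dose (MTD).

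**Working it through.** The plan states no figure on this point, so the check is textual, with two small counts.

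**1. Do the two sentences overlap?**

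| Patient on treatment | First sentence | Last sentence |
|---|---|---|
| Active infection, neutropenic | Do not give | Silent |
| Infection controlled, non-neutropenic, finishing antibiotics | Silent | May give |
| Active infection, non-neutropenic, on antibiotics | Do not give | May give |

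The third row is the conflict. Since the last sentence only permits, withholding complies with both sentences and dosing complies with only one.

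**2. Does another section settle it?**

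- Section 2.1.2.6 excludes "Presence of uncontrolled intercurrent illnesses including but not limited to ongoing or active infection", and section 2.1.2.7 excludes active bacterial infection. Both apply at entry only, and neither defines the term for infections that arise on treatment.
- Section 3.4.3: "Patients with Grade 3 to 4 neutropenia lasting more than one week will receive antimicrobial prophylaxis". It also has antiviral and antifungal prophylaxis considered for patients with a history of such infections, with no neutropenia condition. Neither provision deals with dosing during an infection.
- Section 3.2 defines a DLT as "any grade 3, 4, or 5 toxicity if not incontrovertibly due to disease progression or an extraneous cause", if judged at least possibly related and within the first 28 days, subject to listed exceptions. Section 3.10.1 extends removal to "Unacceptable toxicity occurring at any time during treatment as listed in Section 3.2", and section 3.1 continues treatment only while "Subject is not experiencing any unacceptable toxicity". Together these end treatment for related grade 3 to 5 infections. Grade 1 to 2 and unrelated infections remain.
- Section 3.10.1 also allows removal for intercurrent illness that prevents treatment, or by investigator decision, without saying which infections prevent dosing.
- Sections 3.5.2.6 and 3.5.2.7 give delay limits for neutropenia and thrombocytopenia. Section 3.5.2.5 gives none for infection.

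No section ranks the two sentences.

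**3. On how many occasions could it arise?** From section 3.1, cycle 1 has infusions on days 4, 5, 11 and 18 (4), and cycles 2 to 6 have one each (5): 4 + 5 = 9 per patient. Continuing presupposes having started, so the last sentence clearly reaches the 9 − 1 = 8 infusions after the first. This counts opportunities and is not an expected frequency.

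**4. What room is there for replacement?** From section 10.2, the largest evaluable enrolment is 6 + 6 + 9 = 21 and the accrual ceiling is 24, leaving 24 − 21 = 3 places for all non-evaluable patients, whatever the reason.

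**The case against.** The strongest reply is that the two sentences can be reconciled. First, the last one may be a specific exception to a general rule: it stands in its own paragraph, names both drugs and addresses a defined subgroup. Second, needing antibiotics is not the same as having an active infection, because a patient may be finishing a course after control. Section 2.1.2.6 lends this some support by listing active infection as an example of uncontrolled illness, although it is an entry criterion and also lists ongoing infection. The protocol further contemplates antimicrobial use without active infection, in section 3.4.3 and in the précis, which refers prophylaxis to the manufacturer's recommendations.

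Both readings are reasonable, but neither is written down, and for the patient in the third row they lead to opposite actions. An exception that lifts an unqualified safety prohibition for every non-neutropenic patient on antibiotics should be stated. Elsewhere the protocol says prophylaxis when it means prophylaxis.

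The points about size stand. A compliant course always exists. The trial is run at one institution (section 3.1), and section 7.4.1 has the team meet at least weekly during active treatment to discuss each patient, so inconsistent handling is less likely than in a multi-site trial.

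A reader might infer that investigators are forced into a violation, or that the protocol tells them to dose through severe infection. The documents support neither: withholding is always allowed, and related grade 3 to 5 infections end treatment.

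**Conclusion.** The conflict is real and minor. Section 3.5.2.5 gives two incompatible answers for one identifiable kind of patient, and nothing elsewhere decides between them. In practice it is confined mainly to grade 1 to 2 infections and infections judged unrelated to study drug. How many patients it would reach cannot be calculated, because the protocol gives no rate of infection under this combination.

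A reader might go further and conclude that the MTD determination is compromised. The documents do not support that. The link to the primary endpoint is indirect, through possible non-evaluability after a missed cycle 1 dose, and the protocol already provides for replacement.

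The conclusion assumes that antibiotic treatment carries its ordinary meaning, which includes treating a current infection, and that active infection is not defined in text unavailable for this review.

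**What to change.** Replace the last sentence of section 3.5.2.5 with wording such as: *Obinutuzumab is held while an infection is active; non-neutropenic patients still completing antibiotic treatment may receive it once the infection is clinically controlled in the investigator's judgment. Non-neutropenic patients who require antibiotic treatment may continue rhIL-15.*

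Add delay limits matching section 3.5.2.7: up to one week for the day 11 and day 18 doses of cycle 1, and up to two weeks for a cycle. Doses delayed by the full week would fall on day 11 + 7 = 18 and day 18 + 7 = 25, both inside the 28-day DLT window, so a patient dosed within the limit can still finish cycle 1 treatment in that window.

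This takes the cautious reading. If the sponsor intends an exception for controlled or low-grade infection, it should be written into the prohibition itself.

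The cost is a short text amendment and some late obinutuzumab doses. A DLT-free patient whose infection outlasts the limit, so that a cycle 1 dose is missed, may need replacement from the three places between 21 and 24. The dose levels, the escalation rule, the planned sample size and rhIL-15 dosing in these patients stay as they are.

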3.5.2.6 Neutropenia

Severe and life-threatening neutropenia, including febrile neutropenia, has been reported during treatment with obinutuzumab. Patients with Grade 3 - 4 neutropenia should be monitored frequently with regular laboratory tests until resolution. Anticipate, evaluate, and treat any symptoms or signs of developing infection. Granulocyte colony stimulating factors (G-CSF) may be administered in patients with Grade 3 or 4 neutropenia.

Neutropenia can also be of late onset (occurring more than 28 days after completion of treatment) and/or prolonged (lasting longer than 28 days).

Each cycle may be delayed by up to two weeks until resolution of Grade 3 or 4 neutropenia to Grade 1 or 2. Patients with severe and long lasting (> 1 week) neutropenia are strongly recommended to receive antimicrobial prophylaxis until resolution of neutropenia to Grade 1 or 2. Antiviral and antifungal prophylaxis should be considered.

3.5.2.7 Thrombocytopenia

Severe and life-threatening thrombocytopenia has been reported during treatment with obinutuzumab in combination with chlorambucil or bendamustine. Fatal hemorrhagic events during Cycle 1 have also been reported in patients with CLL treated with obinutuzumab.

Monitor all patients frequently for thrombocytopenia and hemorrhagic events, especially during the first cycle. In patients with Grade 3 or 4 thrombocytopenia, monitor platelet counts more frequently until resolution and consider subsequent dose delays of obinutuzumab and chemotherapy or dose reductions of chemotherapy. Transfusion of blood products (i.e., platelet

Version Date: 09/14/2021

transfusion) may be necessary. Consider withholding concomitant medications which may increase bleeding risk (platelet inhibitors, anticoagulants), especially during the first cycle.

Each cycle may be delayed by up to two weeks until resolution of Grade 3 or 4 thrombocytopenia to Grade 1 or 2. If grade 3-4 thrombocytopenia occurs during Cycle 1, Day 4 and Day 5 doses of Obinutuzumab may still be administered, and Day 11 and Day 18 doses of Obinutuzumab delayed by up to a week until resolution of thrombocytopenia to Grade 1 or 2.

3.5.2.8 Immunization

The safety and efficacy of immunization with live or attenuated viral vaccines during or following obinutuzumab therapy have not been studied. Immunization with live-virus vaccines is not allowed during treatment and until B-cell recovery.

3.6 ON STUDY ASSESSMENTS/EVALUATIONS

After Cycle 1, pre-dose assessments may be performed up to 3 days prior to Day 1 of a cycle, except where otherwise noted. The results from all procedures/tests must be reviewed prior to initiation of each cycle of treatment for consideration of dose modifications and delay of therapy.

Treatment with rhIL-15 and obinutuzumab will continue for six cycles or until disease progression, absent clinical benefit, unacceptable treatment-related toxicity, or other reasons outlined in Section 3.10.1.

Refer to the Study Calendar (Section 3.9) for all tests and procedures to be conducted on study/during treatment. See also Section 5 for all samples to be collected for correlative research. During treatment, it is expected that all laboratory and clinical assessments be conducted at the NIH (including post-treatment imaging evaluations); results from outside NIH will only be accepted at the discretion of the investigator.

3.7 POST-TREATMENT EVALUATIONS

Post-treatment evaluations will be performed at the end of treatment (3-5 weeks after the last dose of protocol treatment). If a subject initiates a new anti-cancer therapy within 30 days after the last dose of trial treatment, the 30-day safety follow-up visit must occur before the first dose of the new therapy.

Unless otherwise noted, follow-up will occur at the following time points: every 3 months (± 2 weeks) for first year after completion of therapy, every 6 months for years 2-5 (± 4 weeks), and then annually thereafter (± 6 weeks) at the discretion of the investigator. Any other evaluations and tests should be performed as clinically indicated.

Upon disease progression or initiation of other anti-cancer therapy, contact will be for survival only until the subject is off study (i.e., every 3 months [±4 weeks]); unless otherwise clinically indicated. See Study Calendar (Section 3.9) for additional information. Any adverse events which are present at the time of discontinuation should be followed in accordance with the safety requirements.

3.8 FOLLOW-UP EVALUATIONS

The following follow-up phases apply to this study at the time points and windows noted above and per the Study Calendar (Section 3.9). Once new anti-cancer therapy has been initiated the subject will move into survival follow-up.

Version Date: 09/14/2021

3.8.1 30-Day Safety Follow-Up Visit

The mandatory Safety Follow-Up Visit should be conducted approximately 30 days after the last dose of trial treatment or before the initiation of a new anti-cancer treatment, whichever comes first. All AEs that occur prior to the Safety Follow-Up Visit should be recorded. Patients with an ongoing, treatment-related AE of Grade > 1 will be followed until the resolution of the AE to Grade 0-1, stabilization of the AE in the opinion of the investigator, or until the beginning of a new anti-neoplastic therapy, whichever occurs first. SAEs that occur within 30 days of the end of treatment or before initiation of a new anti-cancer treatment should also be followed and recorded.

3.8.2 Follow-Up Visits – Prior to Disease Progression

Patients who complete trial treatment without evidence of disease progression will move into the Follow-Up Phase and may be assessed at approximately 6 months and annually thereafter at the discretion of the investigator by radiologic imaging or other clinical assessments to monitor disease status. Every effort should be made to collect information regarding disease status until the start of new anti-neoplastic therapy, disease progression, death, or end of the study.

3.8.3 Follow-Up Visits – Survival/Post-Disease Progression

Once a subject experiences confirmed disease progression or starts a new anti-cancer therapy, the subject moves into the survival follow-up phase and should be contacted (e.g., phone, email, etc.; in-person visit not required) at least every 3 to 6 months collect information on new anti-cancer treatments received and to assess for survival status until death, withdrawal of consent, or the end of the study, whichever occurs first (see Study Calendar).

Abbreviated Title: IL-15+obinutuzumab in CLL Version Date: 09/14/2021

3.9 STUDY CALENDAR

	gui	əu				Study	Study Cycles	es			End of		Post-Treatment Follow-Un	ıt.
Procedure	Sereen	Basel			C				C2-6	,5	Disease Progression	Safety	Follow-Up (Prior to PD)	Survival (Post-PD)
Scheduling Window (Days):	-28 to	0-11	-142	4 (-1)	5 (-1)	8	11 18 (-1) (-1)	1 (-3)	4	∞	Treatment discon/PD ³	Day 30 (+7)	Every 3, 6, or 12 months^4	Every 3 months ⁵
Confirmation of Diagnosis	×													
Physical Exam and ECOG PS ⁶	×	×		×	×	×	X	×	×		×	×	×	
CBC with Differential	×	×	×	×	×	X	X	×	×		×	×	×	
Reticulocyte Count	×	×	×	×	×	×	×	×	×		×	×	×	
Chemistry Panels ⁷	×	×	X	×	×	×	X	×	×		X	X	X	
LDH, Uric Acid, Total Protein		×	×	×	×	×	X	×	×		X	×	X	
PT/INR and aPTT	×	×	X					×			X	X	X	
Thyroid Function (TSH, reflex T3, T4)	×	×	×					×			×			
Urinalysis	×	×	×					×			×			
Pregnancy Test (urine/serum; WOCBP)	×	×	×											
Hepatitis B and C, HIV Antibody, and Karvotype Testing	×													
HLA typing (A, B, C, DR, DQ), Anti- nuclear antibody (ANA), G6PD		×												
CMV, EBV, SPEP, C-reactive Protein (CRP), IGVH mutation analysis, PB		×									X (PD only)			
Interphase FISH panels. Iron panels Folate and B12		×	×		+		-	_						
Serum free light chains, Quantitative IgG		×	×								×	×	×	
Beta-2 microglobulin, Haptoglobin, DAT		×	×					×			×	X	×	
T, B, NK cell subsets		×						×			X	X	×	
CT Scans, Brain MRI ⁹	X	X									X		X	
Flow Cytometry, Bone Marrow Aspiration/Biopsy ¹⁰		X						od)	(post-C3 only)	only)	X			
EKG	X													
Symptoms/Adverse Events Assessment, Concomitant Medication Review	X	X						X			X	X	X	
Research Blood/Tissue Samples ¹¹		×	X	X	×	X		×		×	X	X	X	
Survival Status														×

NOTE: Any other tests should be performed as clinically indicated. See Section 3.4 for drug administration information. See Section 5 for information on research blood samples/correlative studies to be collected.

suspicion for HIV as determined by PI; Hepatitis B and C, karyotype, EKG, PB interphase FISH, and bone marrow aspiration/biopsy (all within 3 months) ¹ Screening and Baseline evaluations should be performed within 28 days prior to enrollment and dosing, respectively, unless otherwise noted and with the following exceptions: Confirmation of diagnosis (no time limit); HIV antibody (at any time, or within 3 months in patients with high risk or clinical NOTE: Any screening tests performed within the specified time frame for baseline do not need to be repeated.

